4.2. Pharmacokinetic Procedures

All the available data from the PK population will be used in the pharmacokinetic analyses. Pharmacokinetic calculations will be performed using non-compartmental methods.

If a subject’s pre-dose concentration is less than or equal to 5% of the C_{max} value for that subject in a period, then the subject’s data from that period without any adjustments will be included in all PK calculations. If the pre-dose value is greater than 5% of the C_{max} in a period, then the data from that period will be excluded, but the data will still be presented in the final study report.

Any sample concentration reported less than the assay limit of quantitation will be set to zero for use in the pharmacokinetic and statistical analyses. Pharmacokinetic and statistical analyses will be conducted on reported values. No concentration estimates are to be calculated for missing values.

Pharmacokinetic parameters (areas, times to peak, and elimination rates) will be calculated using the reported, rather than the scheduled, times of sample collection. Graphical presentations of individual subject results will also use the reported times of sample collection. Graphical presentations of mean results will use the scheduled times.

The following PK parameters will be estimated by non-compartmental methods from plasma samples:

Parameter:	Definition:
C_{max}	Maximum observed plasma concentration.
T_{max}	Time of maximum concentration (h), obtained directly from the observed concentration versus time data.
AUC_{last}	Area under the plasma concentration-time curve from time 0 to time of last measurable plasma concentration, calculated using the linear up/log down trapezoidal method.
AUC_{inf}	Area under the plasma concentration-time curve from 0-time extrapolated to infinity. $AUC_{inf} = AUC_{last} + C_{last} / \lambda_z$; where C_{last} is the last measurable concentration, λ_z is elimination rate constant.
AUC_{ext}	The percentage of the AUC that is extrapolated beyond the last measurable concentration.

λ_z	Apparent plasma terminal-phase elimination rate constant. Estimated by linear regression of log concentration vs. time.
$t_{1/2}$	Terminal-phase half-life, calculated as $\ln(2) / \lambda_z$.
V_z/F	Apparent volume of distribution, terminal phase, for SCP-111, calculated as: $\frac{Dose}{\lambda_z * AUC_{inf}}$
V	Systemic volume of distribution, terminal phase, for IV furosemide, calculated as: $\frac{Dose}{\lambda_z * AUC_{inf}}$
CL/F	Apparent systemic clearance for SCP-111, calculated as: $\frac{Dose}{AUC_{inf}}$
CL	Systemic clearance for IV furosemide, calculated as: $\frac{Dose}{AUC_{inf}}$
F	Bioavailability ($[AUC_{inf} \text{ SC SCP-111}] / [AUC_{inf} \text{ IV furosemide}]$)

A subject profile is to be excluded from AUC_{inf} , AUC_{ext} , λ_z , $t_{1/2}$, V , V_z/F , CL , CL/F , and F for cases that do not exhibit a terminal log-linear phase in the concentration versus time profiles or where the estimated $t_{1/2}$ is physiologically implausible.

4.3. Decimal Precision Convention:

The minimum and maximum statistics will be presented to the same number of decimal places as the original data. The mean and median, Confidence Intervals (CI) will be presented to one more decimal place than the original data, whereas the SD and Standard Error (SE) will be presented to two more decimal places than the original data. P-value will be presented with three decimal places. If p-value is closer to 0, then it should be reported as “<0.001” and if it is closer to 1, then it should be reported as “>0.999”.

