	
Secondary Endpoints:
 
Pharmacokinetics/pharmacodynamics
 
The following pharmacokinetics (PK) parameters will be evaluated for subcutaneous and intravenous furosemide administration:
 
• Maximum observed plasma concentration (C_{max})• Time to C_{max} (T_{max})• Terminal phase elimination rate constant (λ_z), estimated by linear regression of logarithmically transformed concentration versus time data• Terminal elimination half-life ($t_{1/2}$) estimated using the equation $[\ln(2)/\lambda_z]$• Apparent systemic clearance (CL/F)• Systemic clearance (CL)• Apparent systemic volume of distribution (Vz/F)• Systemic volume of distribution (V) 
The following pharmacodynamics (PD) parameters will be evaluated for subcutaneous and intravenous furosemide administration:
 
• Urine output (0-6, 0-8, and 0-12 hours)• Urinary sodium excretion (0-6, 0-8, and 0-12 hours)• Urinary potassium excretion (0-6, 0-8, and 0-12 hours) 
Safety and tolerability
 
Safety
 
Adverse Events (AEs) and Serious Adverse Events (SAEs) will be grouped by body system and summarized. The incidence (number and percentage of subjects) of adverse events and

--	--

	
serious adverse events will be presented overall and by MedDRA System Organ Class and Preferred Term.
 
Injection Site Pain
 
Injection site pain will be assessed using an 11-point scale where 0 is equivalent to no pain and 10 is equivalent to the worst possible pain. For IV administration, the 11-point pain scale will be performed pre-dose after IV needle placement, immediately after 1st dose and 15 and 30 minutes after 1st dose, immediately after 2nd dose and 15 and 30 minutes and 4 and 10 hours after the 2nd dose. For SC administration, the 11-point pain scale will be performed pre-dose, immediately after dose and 15 and 30 minutes and 6 and 12 hours after dose. Pain requiring treatment, withdrawal from the study or discontinuation of study drug will also be recorded as an adverse event (AE).

STUDY DURATION
	
4 months

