6.2.1.3.2. Dosing

For the purpose of assessments and pharmacokinetic sampling times, Day 0, Hour 0 will be defined as the point at which study drug dose is initiated/administered. IV furosemide or SC SCP-111 should be administered according to the randomization schedule. IV furosemide is administered via IV injection as a 40 mg dose over 1 to 2 minutes followed by a second dose of 40 mg over 1 to 2 minutes, 2 hours after the

start of the initial IV dose. SC SCP-111 is administered as a single 80 mg dose via the autoinjector.

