8.4. Pharmacokinetic and Statistical Analysis

Pharmacokinetic parameters will be estimated using noncompartmental methods. Compartmental modeling of the pharmacokinetic data may be conducted.

Furosemide concentrations will be summarized using descriptive statistics (including N, mean, standard deviation (SD), coefficient of variation (CV%), median, minimum, and maximum) for each treatment.

The following PK parameters in table below will be estimated by noncompartmental methods from plasma samples. Actual elapsed time from dosing will be used to estimate all individual PK parameters.

C_{max}	Maximum observed plasma concentration
T_{max}	Time of maximum concentration (h), obtained directly from the observed concentration versus time data.
AUC_{last}	Area under the plasma concentration-time curve from time 0 to time of last measurable plasma concentration
AUC_{inf}	Area under the plasma concentration-time curve from 0-time extrapolated to infinity
AUC_{ext}	The percentage of the AUC that is extrapolated beyond the last measurable concentration
λ_z	Apparent plasma terminal-phase elimination rate constant
$t_{1/2}$	Terminal-phase half life
V_z/F	Apparent volume of distribution, terminal phase, for SCP-111
V	Systemic volume of distribution, terminal phase, for IV furosemide
CL/F	Apparent systemic clearance for SCP-111
CL	Systemic clearance for IV furosemide
F	Bioavailability ($[AUC_{inf} / \text{Dose SC SCP-111}] / [AUC_{inf} / \text{Dose IV furosemide}]$)

Derived plasma PK descriptive statistics will be tabulated by dosing group and summary statistics. Descriptive statistics for PK parameters (C_{max} , T_{max} , AUC_{last} , AUC_{inf} , λ_z , $t_{1/2}$, V , V_z/F , CL and CL/F) will include the arithmetic and geometric mean (for C_{max} , AUC_{last} , and AUC_{inf} , only), CV%, SD of the arithmetic mean, median, minimum, maximum, and N.

Bioavailability of SC SCP-111 will be determined by the logarithmic transformation of the geometric mean ratios of the SC SCP-111 to IV furosemide AUC_{last} and AUC_{inf}

and 90% Confidence Intervals will be determined and should be within 80% and 125% to establish bioequivalence.

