1. TREATMENT

Study Drug:

- Intravenous Furosemide (IV Furosemide): Hospira, furosemide injection, solution 10 mg/mL (NDA 018667) (total dose = 80 mg) administered

intravenously 40 mg over 1 to 2 minutes by IV injection followed by a second dose of 40 mg over 1 to 2 minutes, 2 hours later (reference treatment).

- SCP-111 (furosemide injection), 80 mg/1 mL for subcutaneous administration: Total dose = 80 mg; administered as a subcutaneous injection (test treatment) via an autoinjector.

SCP-111, (furosemide injection), 80 mg/1 mL is a proprietary furosemide formulation that is isotonic and buffered to a neutral pH for subcutaneous administration.

Study Device: SCP-111 Autoinjector is an investigational single-entity drug-device combination product consisting of a prefilled syringe containing 1 mL of SCP-111 (furosemide injection), preloaded into a fixed single dose, disposable, two step mechanical autoinjector designed to administer the full dose to the subcutaneous tissue.

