6. ENDPOINTS

6.1. Pharmacokinetic Endpoints

For IV administration of furosemide injection, USP (reference), PK blood samples will be collected as follows:

- First IV 1 to 2-minute injection dose: Pre-dose and 5, 15, 30, 45 minutes and 1, 1.5, 2 hours after **start** of first IV dose. The sample taken at 2 hours will be drawn immediately prior to the start of the second IV dose.
- Second IV 1 to 2-minute injection dose (new clock for PK sampling starts upon the start of administration of second IV dose): 5, 15, 30, 45 minutes and 1, 1.5, 2, 3, 4, 6, 8 and 10 hours after **start** of second IV dose.

For the SC administration of SCP-111 (test), PK blood samples will be collected as follows:

- Pre-dose and 5, 15, 30, 45 minutes and 1, 1.25, 1.5, 2, 3, 4, 5, 6, 8 and 12 hours after the SC injection

Individual pharmacokinetic parameters for furosemide will be summarized with descriptive statistics. Pharmacokinetic parameters including:

- the maximum observed plasma concentration (C_{max}),
- the area under the plasma concentration versus time curve from time 0 (pre-dose) to the last quantifiable time point (AUC_{last}),
- the AUC from time 0 (pre-dose) to time infinity (AUC_{inf}),
- the time to C_{max} (T_{max}), the terminal phase elimination rate constant (λ_z), the terminal elimination half-life ($t_{1/2}$) for both SC SCP-111 (test) and IV furosemide (reference),

- the apparent systemic clearance (CL/F) for SC SCP-111 and systemic clearance (CL) for IV furosemide,
- the apparent systemic volume of distribution (Vz/F) for SC SCP-111

Systemic volume of distribution (V) for IV furosemide will be calculated using non-compartmental analysis.

Bioavailability of SC SCP-111 will be determined based on the geometric mean ratios of AUC_{last} and AUC_{inf} of IV furosemide (reference) and SC SCP-111 (test) and 90% confidence intervals on these ratios.

Geometric mean ratios of C_{max} of IV furosemide (reference) and SC SCP-111 (test) and 90% confidence intervals on these ratios will also be determined.

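### IV Tmax is one overall maximum from a two-injection profile, so it will cluster near 0.083 h and 2.083 h and cannot be read beside SC Tmax as time to peak

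*SAP*

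**What the plan says.** The test is a single 80 mg SC injection. The reference is 40 mg IV followed by another 40 mg IV 2 hours later (SAP, Treatment section; Protocol 3.1.1).

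SAP 4.2 defines Cmax as "Maximum observed plasma concentration" and Tmax as "Time of maximum concentration (h), obtained directly from the observed concentration versus time data". Each is one value per profile. Neither document defines these parameters per injection or gives a rule for a profile with two peaks. SAP 4.2 treats Tmax as a time to peak, and SAP 9.1 summarises it by arithmetic mean, SD, CV%, median, minimum and maximum.

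Tmax and Cmax are secondary endpoints for both routes. The Protocol synopsis introduces the list with "The following pharmacokinetics (PK) parameters will be evaluated for subcutaneous and intravenous furosemide administration".

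Three statements bear on the clock:
- Protocol 6.2.1.3.2: "Hour 0 will be defined as the point at which study drug dose is initiated/administered".
- SAP 6.1, on IV sampling: "new clock for PK sampling starts upon the start of administration of second IV dose".
- Protocol 8.4: "Actual elapsed time from dosing will be used to estimate all individual PK parameters". It does not say which of the two IV injections is meant.

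IV samples are drawn 5 minutes after the start of each injection. For the end of the first interval, SAP 6.1 says: "The sample taken at 2 hours will be drawn immediately prior to the start of the second IV dose".

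**The concern.** After an IV injection of 1 to 2 minutes, the highest scheduled sample should be the first one, at 5 minutes. The reference profile has two such peaks 2 hours apart, and the second sits on whatever remains of the first dose. Taking one maximum over the whole profile therefore asks which of two early samples was higher. The time attached to the answer is set by the dosing schedule.

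That value goes into the same table as SC Tmax, under the same label. A reader could see an intravenous injection with a time to peak of 1.5 to 2 hours and judge SC absorption against it. The mean makes this worse, because averaging two clusters 2 hours apart can give a time at which nobody peaks. The unsettled clock adds a second problem: the same second-injection peak could be programmed as 2.083 h or as 0.083 h.

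**Working it through.** **Plan's own figure.** The documents state no expected Tmax or Cmax, so there is none to reproduce. The 18 completers are used below only to turn percentages into counts. That number was sized on AUCinf. Half of the 31.6% total CV is 15.8%. With a true ratio of 0.95, an exact two one-sided tests calculation for a 2x2 crossover gives 93.2% power at 18, consistent with the stated minimum of 90%. Nothing here changes it.

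**Inputs from the documents.** Two equal IV doses at 0 and 2 h; first sample 5 minutes (0.083 h) after the start of each; 18 completers.

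**Inputs assumed, because the documents do not give them.** Carry-over r is the concentration left from injection 1 at 2 h 5 min, divided by its concentration at 5 min. The range is 0.05 to 0.40. The per-sample CV covers assay error and timing, with range 5% to 20%. The model takes r and the CV as common to all subjects and the errors as independent and log-normal.

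**Step 1, times.** On the Hour 0 clock the two candidate peaks are at 0.083 h and 2 + 0.083 = 2.083 h. Reported sample times are used, so values will scatter closely around these two.

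**Step 2, which peak is higher.** By superposition, expected peak 2 = expected peak 1 × (1 + r). With s = √ln(1 + CV²), the chance that the second is observed higher is

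p = Φ( ln(1 + r) / (√2 · s) ).

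For r = 0.10 and CV 10%, ln(1.10) = 0.0953 and s = 0.0998, so p = Φ(0.0953 / 0.1411) = 0.75.

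Share of subjects with IV Tmax near 2.083 h:

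| r | CV 5% | CV 10% | CV 20% |
|---|---|---|---|
| 0.05 | 76% | 64% | 57% |
| 0.10 | 91% | 75% | 63% |
| 0.20 | 99.5% | 90% | 74% |
| 0.40 | 100% | 99% | 89% |

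The rest fall near 0.083 h. At r = 0.10 and CV 10%, that is 13.5 of 18 subjects near 2.083 h and 4.5 near 0.083 h on average.

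**Step 3, the planned summaries.** Mean = 0.083 + 2p and SD = 2√(p(1 − p)). At p = 0.75:
- Mean = 0.75 × 2.083 + 0.25 × 0.083 = 1.58 h
- SD = 2 × √0.1875 = 0.87 h

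A time of 1.58 h lies between the 1.5 h and 2 h samples, where concentrations after injection 1 are falling. Over the whole table the mean runs from about 1.2 to 2.08 h. In simulated studies of 18 subjects, the median was 2.083 h with probability 0.64 to 1.0.

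**Step 4, sensitivity to sampling time.** In illustrative two-compartment profiles (assumed), drawing the 5-minute sample at 4 instead of 6 minutes changes the level by about 6% to 22%. At r = 0.10 the expected gap between the peaks is 10%, so ordinary timing variation can decide which injection supplies Tmax.

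**Step 5, the clock.** If a second-injection peak is timed on the restarted clock, it is recorded as 0.083 h, and essentially every IV Tmax becomes about 0.083 h. The two readings of the text therefore differ by 2 hours for every subject who peaks after injection 2.

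**Step 6, Cmax.** By the same superposition, the expected second peak is (1 + r)/2 of the peak after a single 80 mg IV injection. For r of 0.03 to 0.33, the range in the illustrative profiles, this is 1.03/2 = 0.515 to 1.33/2 = 0.665. Taking the larger of two noisy peaks adds about 0% to 9% to IV Cmax over the second peak, for r of 0.05 to 0.40 and CV of 5% to 20%.

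**The case against.** A reader might go further in three directions, and the documents do not support any of them.

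- **That IV Tmax must be 2.08 h by construction.** It is only the likely median. At low carry-over and high noise, over 40% of subjects would fall near 0.083 h. The figure also presumes the Hour 0 clock. That is the natural reading, since AUC runs from time 0, but it is not stated for Tmax.
- **That a formal comparison of absorption rate is compromised.** None is planned. SAP 9.1 restricts the parameter ANOVA to Cmax, AUClast and AUCinf, so Tmax is descriptive only. The 80% to 125% criterion in SAP 9.1.1 covers the two AUCs, and the Cmax ratio has a 90% interval but no acceptance limits.
- **That the SAP hides what IV Cmax is.** It states the split regimen in the treatment section, the primary objective and SAP 6.1, where the Cmax ratio is introduced. Overall Cmax is a valid measure of peak exposure for the regimen as dosed.

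It can also be said that the two peaks will be visible elsewhere. Concentrations at each scheduled time are analysed, individual profiles are plotted, and the Tmax table already includes median and range. Per-injection values could be derived after the fact. Finally, IV Cmax for one injection beside SC Cmax sets 40 mg against 80 mg, which is a mismatch of its own.

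These points limit the consequence and should shape the fix. They do not make the planned IV Tmax interpretable. Followed exactly, the rule yields a number for a named secondary endpoint that does not mean what its label says.

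**Conclusion.** The point holds as a reporting defect in a secondary endpoint. IV Tmax under SAP 4.2 and 9.1 will record which injection gave the higher sample, in two clusters near 0.083 h and 2.083 h. Its mean may fall where no subject peaks, and its clock is not settled. It cannot be set beside SC Tmax as time to peak.

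The two cluster times follow from the schedule alone, on the Hour 0 clock. That the later one is favoured needs only some carry-over. The size of the split (57% to 100% near 2.083 h over the ranges used) rests on assumed carry-over and per-sample CV, and the study itself will supply the real values.

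The AUC-based primary conclusion and the sample size are unaffected. Nothing here bears on dosing or on the sampling schedule.

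**What to change.** In SAP 4.2, 6.1 and 9.1:

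1. State that overall IV Tmax runs from the start of the first injection.
2. Add Cmax1 and Tmax1 for 0 to 2 h, and Cmax2 and Tmax2 after the second injection, with Tmax2 timed from the start of that injection. Present them descriptively and note that each injection is 40 mg, so they are not read as dose-matched to SC.
3. Keep overall IV Tmax, which is a named parameter, but report it as median, range and number of subjects at each peak. Drop its mean, SD and CV%.
4. Keep overall Cmax and the SC/IV ratio with its 90% interval. Label them as regimen-level peak exposure, with a footnote that the IV value is the larger of two injection peaks, usually the second 40 mg plus residual.

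The SAP takes precedence over the protocol (SAP 9), so the change belongs there. The cost is a few sentences and a few table rows. Both injections already have samples at 5, 15, 30 and 45 minutes, and the 2 h sample precedes the second injection, so no new data are needed.

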4.4. HANDLING OF MISSING DATA

No plasma concentration estimates will be imputed for missing values. Missing values will be treated as if they were not scheduled for collection and only those

samples with reported concentration values will be included in the pharmacokinetic and statistical analysis.

Missing values for urine collections will not be imputed. Any subject with a missing value for any subinterval (e.g. 0-1 hour) involved in the 0-6, 0-8 or 0-12 results will be excluded from statistical analyses for the interval affected.

No imputation of missing data will be done for any other data. To handle missing or partial AE and concomitant medication dates, the following rules in 5.4.1 will be applied.

4.4.1. For Partial Start Dates:

1. If the year is unknown, then do not impute the date but assign a missing value.
2. If the month is unknown, then:
 - i. If the year matches the year of the first dose date, then impute the month of the dose date.
 - ii. Otherwise, assign "January."
3. If the day is unknown, then:
 - i. If the month and year match the month and year of the first dose date, then impute the day of the dose date.
 - ii. Otherwise, assign "01."

4.4.2. For Partial End Dates:

1. If the year is unknown, then do not impute the date but assign a missing value.
2. If the month is unknown, then assign "December."
3. If the day is unknown, then assign the last day of the month.

After implementing the rules above, to determine whether AEs (or medications) with missing start or stop dates are pre-treatment or on/after first or second treatment, the following strategy will be used:

1. If both start date and stop date are missing, then the most conservative approach is taken, and the AE (or medication) is classified as treatment emergent (or concomitant medication).
2. If the start date is missing but the stop date is not missing and is on or after the day of study dose administration for Period 1 or 2, then the most conservative approach is taken, and the AE (or medication) is treatment emergent (or concomitant medication).
3. If the start date is missing but the stop date is not missing and is before the day of study dose for Period 1 and after the date of signed informed consent, then the AE (or medication) is not a TEAE (or prior medication).

4. If the start date is not missing but the stop date is missing, then the most conservative approach is taken, and medication is concomitant while the AE is defined by start date.

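### The SAP has no rule for a missing 2-hour sample before the second IV dose, so its AUC method would overstate that subject's IV exposure

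*SAP*

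**What the plan says.** **Missing samples.** SAP 4.4 states "No plasma concentration estimates will be imputed for missing values" and "Missing values will be treated as if they were not scheduled for collection". SAP 4.2 repeats the bar: "No concentration estimates are to be calculated for missing values".

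**Integration.** SAP 4.2 defines AUClast from time 0 to the last measurable concentration, "calculated using the linear up/log down trapezoidal method". Parameters such as areas "will be calculated using the reported, rather than the scheduled, times of sample collection". Neither document splits the area at the second IV dose.

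**IV sampling.** In SAP 6.1 the samples after the first injection are "Pre-dose and 5, 15, 30, 45 minutes and 1, 1.5, 2 hours after" the start of that dose. "The sample taken at 2 hours will be drawn immediately prior to the start of the second IV dose". The next sample is 5 minutes after the second injection starts, which is 2 h 05 min on the study clock. The SAP says that a "new clock for PK sampling starts upon the start of administration of second IV dose", but this governs sampling times and does not mention integration.

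**Which profiles count.** The PK and Bioavailability populations (SAP 8) require sufficient samples for estimating the parameters. Sufficient is not defined.

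**The concern.** Dropping a missing value is close to harmless in a profile that only falls after its peak, because log-linear interpolation between the neighbours follows the curve. The IV profile is different: it falls to 2 h, then jumps at the second injection. The 2-hour sample is the only one that marks the bottom of that jump. Without it, the adjacent pair is 1.5 h and 2 h 05 min. That pair rises, so the linear-up rule applies across 35 minutes, about 30 of which were really a decline.

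The analyst cannot repair this within the plan, because any estimate is barred. IV AUClast and AUCinf are the denominators of both primary ratios, and IV AUCinf is also the denominator of individual F. The affected subject's SC/IV ratio is pushed down, and the outlying difference enlarges the residual error behind the 90% confidence intervals.

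**Working it through.** **1. The plan's own figure.** The sample-size text (SAP, Sample Size; protocol 8.1) gives a total CV of 31.6% for IV AUCinf and takes intra-subject variability as about half of total. Halving the CV gives 31.6/2 = 15.8%. Exact two one-sided tests for a 2x2 crossover (limits 0.80 to 1.25, 0.05 per side, n = 18) give power of 93.2% at a true ratio of 0.95 and 93.8% at 1.05. The stated 18 subjects with at least 90% power therefore reproduces.

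**2. Inputs for the AUC check.** From the documents: two 40 mg IV doses 2 h apart, the 20 scheduled IV sample times (8 up to and including 2 h, 12 after), and the linear-up/log-down rule. Assumed, because the documents give no kinetics: one-compartment half-lives of 0.25 to 3 h, and two-compartment profiles with distribution half-life 5 to 30 min, terminal half-life 1 to 3 h and fast fraction 0.5 to 0.9. The injection is taken as 1.5 min.

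**3. One case by hand.** One compartment, half-life 1 h, each injection treated as instantaneous and raising the concentration by 1 unit, k = ln 2 = 0.6931 per h.

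- C(1.5 h) = 2^-1.5 = 0.3536
- C(2 h) = 2^-2 = 0.2500
- C(2 h 05 min) = 2^-2.0833 + 2^-0.0833 = 0.2360 + 0.9439 = 1.180

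With the 2 h sample:

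- log-down, 1.5 to 2 h: (0.3536 - 0.2500)/0.6931 = 0.149
- linear-up, 2 h to 2 h 05 min: 0.0833 x (0.2500 + 1.180)/2 = 0.060
- sum: 0.209

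Without it:

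- linear-up, 1.5 h to 2 h 05 min: 0.5833 x (0.3536 + 1.180)/2 = 0.447

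The excess is 0.447 - 0.209 = 0.238. The complete-sample AUC to 12 h is:

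- 0 to 5 min: 0.0833 x 0.9439/2 = 0.039
- 5 min to 2 h: (0.9439 - 0.2500)/0.6931 = 1.001
- 2 h to 2 h 05 min: 0.060
- 2 h 05 min to 12 h: (1.180 - 0.001)/0.6931 = 1.701
- total: about 2.80

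The overstatement is 0.238/2.80 = 8.5%.

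**4. Range over the assumptions, 2 h sample missing, relative to the complete-sample AUC.**

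| One-compartment half-life (h) | IV AUC |
|---|---|
| 0.25 | +31.2% |
| 0.5 | +16.6% |
| 0.75 | +11.3% |
| 1 | +8.5% |
| 1.5 | +5.7% |
| 2 | +4.4% |
| 3 | +3.1% |

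The two-compartment grid (80 settings) gives +4.8% to +32.9%. Direction is upward in every setting.

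**5. Against true AUC.** The complete-sample AUC is itself 0.7% to 8.3% low in the one-compartment cases. Relative to the true model AUCinf, the error with the trough missing is +2.2% to +20.3%.

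**6. Other samples.** In the one-compartment model (half-lives 0.25 to 2 h), omitting the 1.5 h sample changes AUC by about 0%. Omitting the 2 h 05 min sample changes it by -1.5% to -12.0%. The 2 h sample gives the larger error at every half-life tried.

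**7. Effect on the trial.** One affected subject of 18 multiplies the geometric mean ratio by exp(-ln(1 + e)/18).

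- e = 0.031: 0.998, or -0.2%
- e = 0.329: 0.984, or -1.6%

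Simulated power with one affected subject, CV 15.8%, n = 18:

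| Error in that subject | True ratio 0.95 | True ratio 1.05 |
|---|---|---|
| none | 93.1% | 93.8% |
| +11% | 91.3% | 94.7% |
| +31% | 87.3% | 95.7% |

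**8. With the proposed rule.** Extrapolating the 2 h value log-linearly from the 1 h and 1.5 h samples, C(2) = C(1.5) x [C(1.5)/C(1)], brings the error against the complete profile to 0.0% (one-compartment) and between -0.3% and 0.0% (two-compartment).

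**The case against.** **Size.** A reader might infer a fixed double-digit bias. Certain assumed clearances and volumes do give 11% to 31%, but nothing in the documents selects them. That band corresponds to one-compartment half-lives of about 0.77 h down to 0.25 h, and only 59% of the two-compartment settings fall inside it. Nor is it an error against true AUC, where the excess is smaller. This objection stands, and it is why the range is tied to assumptions.

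**Likelihood.** Only one of 20 IV samples triggers the problem, and neither document gives a missing-sample rate. The draw is tied to the second dose, site staff give both doses to domiciled subjects, an indwelling catheter is allowed (protocol 6.2.2.6), and assessments due at the same time may be done just before the PK draw (protocol 6.2). This also stands: the point is conditional.

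**Direction.** The error lowers SC/IV. At a true ratio of 0.95 it makes equivalence harder to show, and at 1.05 it slightly raises power. It is not an evident route to a false claim, and a reader should not infer one.

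**Existing safeguard.** The sufficient-samples condition could be read to exclude such a profile. It is undefined, and 19 of 20 values would remain, so it cannot be relied on. Using it here would be an unspecified decision in an open-label study.

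**Late samples.** A reader might extend the point to a sample drawn after the second injection has begun. That sample has a reported value and is used at its actual time, so the missing-value rule does not govern it.

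**Conclusion.** The point holds as a conditional gap in the SAP. The mechanism and its upward direction follow from the stated rules: no estimate, missing treated as unscheduled, and a single linear-up/log-down integral across two doses.

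The size does not follow from the documents. Under the assumed profiles it is about 3% to 33% of the complete-sample IV AUC for the affected subject, 3% to 9% at one-compartment half-lives of 1 h or more, and less against true AUC. For the trial, one such subject of 18 shifts the geometric mean ratio by about -0.2% to -1.6%. Power stays above the planned 90% in the milder simulated case and falls below it only with a large error and a true ratio of 0.95. If the draw is never missed, nothing changes. Low to moderate priority.

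**What to change.** Add one exception to SAP 4.2 and 4.4 for the IV period, before the analysis. If the 2 h pre-second-dose sample is missing:

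- set the concentration at the recorded start of the second dose by log-linear extrapolation from the last two reported samples after the first dose;
- integrate the two dosing intervals separately;
- flag the profile, and repeat the primary analysis without it.

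Excluding the profile from the primary analysis by a stated rule is a workable alternative, provided it is fixed in advance. The cost is a few sentences and no extra samples. The small downside is one estimated value where the SAP now allows none.
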